4.2 ABLATION PROCEDURES

Standard Ablation Technique for Ventricular Arrhythmias:

The standard ablation procedure will be performed using the Biosense-Webster Thermocool SF catheter (Diamond Bar, CA, USA). Hemodynamic support to allow for entrainment mapping may be employed with either an intra-aortic balloon pump or with a percutaneous left ventricular assist device. All mapping will be performed with a hybrid magnetic/impedance-based mapping system (Carto, Biosense Webster, Diamond Bar, CA). LV endocardial and epicardial mapping will be performed by utilizing a transseptal and subxiphoid puncture approach, respectively. Prolonged, split, or isolated late potentials will be tagged. For unipolar RF, power will be set to 30–50 W at 30-cm³ irrigation, targeting an impedance drop of >10 Ω. In the epicardium, power will be set to 15–30 W with 5-ml/min irrigation. The use of the percutaneous left ventricular assist device in patients with ventricular tachycardia (VT) allows for prolonged mapping during VT. Termination during VT will therefore be the preferred initial strategy for these patients, followed by substrate modification. The procedural end point will be non-inducibility of VT.

Intramural Needle Ablation of Ventricular Arrhythmias:

INA will be performed with Intramural Needle Ablation catheter, a retractable needle-tipped catheter (Biosense Webster, Inc., Diamond Bar, CA, USA). The catheter will be positioned at locations determined on the basis of activation or entrainment mapping. Saline solution (0.9% NaCl, 19°C) will be infused through the needle into the myocardium at 1 mL/min for 60 seconds using an automatic injector (Mark V, Medrad, Pittsburgh, PA, USA). Ablation will be initiated with RF energy (500 kHz, Stockert-70 RF Generator, Stockert GMBH, Freiburg, Germany) which will be delivered between the needle and a skin patch electrode. Power will be manually titrated between 30-50 W (limiting catheter tip temperatures to < 60°C) over 60-90 seconds for an impedance drop of up to 30-40 Ω. Ablation will be terminated or the power down-titrated if a sudden rise in temperature or a rapid fall or rise in impedance is seen.

5 SCHEDULE OF TREATMENT AND TESTS

TABLE 1: SCHEDULE OF TREATMENTS AND TESTS:

	Baseline (within 30 days)	Procedure	Discharge	Telephone Follow-up (2 weeks +/- 3 days)	Follow-up Visit (6mo, +/- 2 weeks)
Type of visit	Office	Hospital		N/A	Office
Informed Consent	X				
Brief History & Physical	X				X
Blood Laboratory Testing: CBC, Electrolytes, BUN/Creatinine, BNP, INR, LFTs	X				X (as indicated)
TTE	X (within 3 months)				
CT/MRI (optional)	X (within 3 months, if done)				
*24-Hour Ambulatory Monitor	X (within 3 months)				X
ICD Interrogation	X				X
Ablation Procedure		X			
EKG	X				X
Medications	X	X	X	X	X
Adverse Events		X	X	X	X

*24-hour ambulatory monitoring will only be required for those undergoing ablation for frequent ventricular arrhythmia (defined as unifocal PVCs, couplets, non-sustained VT) that is causing a decline in LV ejection fraction to $\leq 40\%$.

Patients whose VT is successfully treated with standard ablation once enrolled will be placed in a registry and will continue to be followed throughout the study, adhering to the same post-procedure schedule as the patients who underwent intramural needle ablation. Patients whose VT is not inducible and no VT ablation is performed during the procedure will also be considered screen failures. No follow-up will be performed with subjects who have no VT ablation during the procedure.

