7 STUDY SUBJECTS

7.1 INCLUSION CRITERIA

1. The study will include patients with any of the following criteria: a) monomorphic ventricular tachycardia (VT); b) frequent ventricular arrhythmia (defined as unifocal PVCs, couplets, non-sustained VT) with a PVC burden $\geq 13\%$, or is causing a decline in left ventricular (LV) ejection fraction to $\leq 40\%$; or c) previous failed ablation for one or more of the criteria above.
2. ≥ 16 years of age.
3. Left ventricular (LV) ejection fraction $> 10\%$ as estimated by echocardiography, CT/MRI, contrast ventriculography, or radionuclide imaging within the past 90 days.
4. Clinical indication for catheter ablation of VT
5. Intramural ventricular arrhythmias not terminable with standard ablation once enrolled in the Intramural Needle Ablation study or previous failed ablation within 6 months prior to enrollment.
6. Ability to understand the requirements of the study and sign the informed consent form. For potential patients aged < 18 , parental consent will be required along with subject assent.
7. Able and willing to comply with all pre-, post-, and follow-up testing and requirements.
8. Projected lifespan greater than 1 year.

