7.2 EXCLUSION CRITERIA

1. History of MI or CABG within 6 weeks.
2. NYHA Class IV CHF.
3. Patients with idiopathic ventricular arrhythmias defined as VT or PVCs that occur without evidence of structural heart disease and that are not causing significant depression of LV function.
4. Women known to be pregnant or to have positive beta-HCG.

5. Definite protruding left ventricular thrombus on pre-ablation echocardiography or other imaging modalities.
6. Contraindication to heparin
7. Allergy to radiographic contrast dye.
8. Unstable angina that is not due to frequent or incessant VT.
9. Acute non-cardiovascular illness or systemic infection.
10. Thrombocytopenia (platelet count < 50,000 mm³) or coagulopathy.
11. Cardiogenic shock unless it is due to incessant VT.
12. Unable to sign consent.
13. Projected lifespan of < 1 year.

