10 STUDY PROCEDURES

10.1. PRE-PROCEDURE EVALUATION

Patients will be consented for the study in either the inpatient or outpatient setting. The consent will detail the use of RF energy as part of standard of care in all patients undergoing VT ablation, and INA ablation as an experimental procedure employed only if patient had an unsuccessful ablation within six months prior to enrollment or if the index ablation procedure proves unsuccessful. Unsuccessful ablation is defined as the inability to terminate ventricular arrhythmias or ventricular arrhythmias that are still inducible following ablation.

The following tests and procedures will occur before the ablation as a routine part of pre-procedural medical assessment (all done within 30 days prior to procedure unless noted below):

- Recording of patient medical history (including details of VT both clinical/ICD)
- Recording medication history (including all anti-arrhythmic drugs used and duration of use)
- Obtain β-HCG in females of child bearing age the morning of the procedure as per usual clinical practice
- Baseline assessment of arrhythmia burden and type:
 - Office/inpatient records, ICD interrogation report

- For patients being considered for PVC ablation only: 24-Hour Holter monitoring (within three months)
- Review pre-procedural imaging (within three months): MRI/CT (optional), TTE.
- Baseline laboratory, including complete blood count, standard electrolyte panel, renal function, and brain natriuretic peptide levels.
- Consent must be obtained before the VT ablation procedure.

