10.4 POST-PROCEDURE

10.4.1 POST-PROCEDURE FOLLOW UP

- All patients will be monitored to verify vascular hemostasis prior to discharge from the hospital.
- The majority of patients will receive either warfarin or a novel oral anti-coagulant (dabigatran, rivaroxaban, or apixaban) for 4-6 weeks post-procedure. Those patients with less extensive ablations may receive oral aspirin (81-325 mg daily) or clopidogrel (75 mg daily). These decisions will be made at the discretion of the primary operator per current guidelines.
- A proton pump inhibitor is recommended for any significant esophageal temperature rises noted during the procedure as determined by the treating physician. However, if the esophageal temperature is noted to have been $\geq 41.0^{\circ}\text{C}$, a proton pump inhibitor is required for a minimum of 4 weeks following the ablation procedure.
- Medication and adverse event review will be performed prior to discharge.
- Complications including vascular, stroke, heart failure, pericardial effusion, tamponade, bleeding, and death will be documented.
- The total number of episodes of VT, ATP, and shocks will be documented at all visits.

- The follow-up includes:
 - 2 weeks: Telephone follow up
 - Assessment for adverse events or recurrent arrhythmia.
 - 6 months: In-office follow up
 - History and Physical
 - Electrocardiogram
 - ICD interrogation (may be trans-telephonic)
 - Review of medications and adverse events
 - For PVC ablation patients only: 24-Hour Holter monitoring

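### Table 1 and Section 10 disagree on who needs 24-hour monitoring, so some patients may have no 6-month beat count for the co-primary efficacy endpoint

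*Combined protocol and SAP*

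**What the plan says.** Three places state who has the 24-hour recording.

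- **Section 5, Table 1 footnote:** "24-hour ambulatory monitoring will only be required for those undergoing ablation for frequent ventricular arrhythmia". After defining that arrhythmia as unifocal PVCs, couplets and non-sustained VT, the sentence adds a condition: "that is causing a decline in LV ejection fraction to" 40% or below. The asterisk is on the monitor row, so the condition covers both the baseline and the 6-month recording.
- **Section 10.1 (baseline):** "For patients being considered for PVC ablation only: 24-Hour Holter monitoring (within three months". No LVEF condition. The same list gives "Office/inpatient records, ICD interrogation report" as further sources for baseline arrhythmia burden.
- **Section 10.4.1 (6 months):** "For PVC ablation patients only: 24-Hour Holter monitoring". No LVEF condition.

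Eligibility is wider than the footnote. Section 7.1, criterion 1b, admits "frequent ventricular arrhythmia (defined as unifocal PVCs, couplets, non-sustained VT) with a PVC burden" of at least 13%, or arrhythmia that has brought LVEF to 40% or below; either route is enough. Section 7.2, criterion 3, excludes only arrhythmias that "occur without evidence of structural heart disease and that are not causing significant depression of LV function".

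The efficacy endpoint in Section 6.1 uses a threshold of 5000 ventricular beats in 24 hours for PVCs, couplets and non-sustained VT. It accepts symptoms, device interrogation or ambulatory monitoring as sources and does not mention LVEF.

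**The concern.** A coordinator working from the schedule table and one working from Section 10 would order different tests for the same patient. The test supplies data for a co-primary endpoint. A 24-hour count not taken in the 6-month window cannot be obtained later. If the footnote is applied, patients who entered on PVC burden without an arrhythmia-related fall in LVEF could reach 6 months with nothing to compare with the 5000-beat threshold, while patients with such a fall would have a count. The endpoint would then be ascertained differently in two parts of one cohort. Registry patients are exposed too, because Sections 5 and 9 put them on the same post-procedure schedule.

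**Working it through.** The plan has no figure to reproduce and no arithmetic applies. The check sets the three monitoring rules against the eligible groups.

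| Reason for ablation | Table 1 footnote | Sections 10.1 and 10.4.1 | Result |
|---|---|---|---|
| PVCs, arrhythmia causing LVEF to fall to 40% or below | Required | Required | Consistent |
| PVCs, burden at least 13%, no such fall | Not required | Required | **Conflict** |
| Couplets or non-sustained VT, with such a fall | Required | Unclear: only PVC ablation is named | Terms differ |
| Couplets or non-sustained VT, no such fall | Not required | Unclear | Terms differ |
| Sustained monomorphic VT only | Not required | Not required | Consistent |

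**Can the conflict row contain patients?** Criterion 1b joins its two routes with *or*, and the footnote carries only the second. Exclusion criterion 3 has two parts joined by *and*: no structural heart disease, and no significant LV depression caused by the arrhythmia. A patient with structural heart disease fails the first part and is not excluded. So a patient with structural heart disease, a burden of at least 13% and LVEF above 40% is eligible and outside the footnote. So is one whose LVEF is 40% or below for a reason other than the arrhythmia. The row is not empty by design.

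**Does the endpoint apply to them?** Yes. The beat-count criterion in Section 6.1 has no LVEF condition.

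**Could another listed source supply the count?**

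- Symptoms give no number of beats.
- Device interrogation is scheduled at 6 months, but the documents do not say whether it yields a 24-hour ventricular beat count. Section 10.4.1 asks for tallies of VT episodes, anti-tachycardia pacing and shocks, and no inclusion criterion requires an ICD.
- At baseline the position is easier: records and ICD reports are named sources, and entry on burden presupposes some estimate of it.

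The exposure is therefore mainly at 6 months.

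**Does any text settle precedence?** None was found in Section 5, 6 or 10.

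**The case against.** The best defence is that the two texts can be obeyed together. The footnote limits what is required and does not forbid the test. Section 10.4.1 already lists the 6-month Holter for PVC ablation patients, and there is one site. A team that reads both will obtain the count. This stands, and it makes the consequence conditional: data are lost only if Table 1 is followed in place of Section 10. It does not remove the contradiction about what is required.

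A second defence is that Section 6.1 accepts sources other than monitoring. That is so, and the documents do not say interrogation cannot give a count. They do not say it can either, so it cannot be relied on to fill the gap.

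A third is that little statistical machinery rests on the count. Section 8 sets the sample size by feasibility, and Section 17 reports percentages. This limits the weight of the point; the percentage still depends on how each patient is classified.

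A reader might go further and infer that the efficacy result will be incomplete, or biased towards success. The documents support neither: they do not show which text the site follows, how many patients are in dispute, or how those without a count would be classified. A reader might also see a separate gap for patients entering through "previous failed ablation for one or more of the criteria above". There is none, because the footnote turns on the reason for ablation, not the entry route.

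**Conclusion.** The inconsistency is established by the text: the footnote carries an LVEF condition that Sections 10.1 and 10.4.1 lack, and eligible patients can fall between them. The effect on the endpoint is a risk, not a demonstrated loss. It assumes that Table 1 is followed over Section 10 and that interrogation does not supply a 24-hour count. Its size is unknown. Section 8 expects about 70 evaluable needle-ablation patients from 200 enrolled, but does not divide them by indication or LVEF. No direction of bias can be stated. The point should be corrected because it touches a co-primary endpoint and the correction is cheap; it does not by itself undermine the design.

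**What to change.** Reconcile the Table 1 footnote with Sections 10.1 and 10.4.1 by removing its LVEF-only restriction. Every patient ablated for frequent ventricular arrhythmia and assessed on the beat-count criterion would then have the 24-hour recording. The 6-month recording matters most, since baseline burden has other named sources.

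Use one term for this group in the footnote and both Section 10 entries: frequent ventricular arrhythmia, meaning unifocal PVCs, couplets and non-sustained VT, the arrhythmias named in Section 6.1.

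The cost is one footnote edit and two wording changes. Section 10 already lists the recording for PVC ablation patients, so nothing is added for them. The downside is that some patients ablated for couplets or non-sustained VT, in unknown number, may need a recording that Section 10 does not clearly require at present.

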Patients will be excluded from the trial if: 1) history of MI or CABG within 6 weeks; 2) Class IV HF; 3) Idiopathic ventricular arrhythmias defined as VT or PVCs that occur without evidence of structural heart disease and that are not causing significant depression of LV function; 4) pregnant; 5) Definite protruding left ventricular thrombus on pre-ablation echocardiography or other imaging modalities; 6) contraindication to heparin; 7) allergy to radiographic contrast dye; 8) unstable angina that is not due to frequent or incessant VT; 9) acute non-cardiovascular illness or systemic infection; 10) thrombocytopenia (platelet count $< 50,000 \text{ mm}^3$) or coagulopathy; 11) cardiogenic shock unless it is due to incessant VT; 12) unable to sign consent; 13) projected lifespan of < 1 year. Patients are considered enrolled once consented. Patients who do not undergo ablation of ventricular arrhythmias within 90 days of enrolling will be considered to be screen failures. Patients successfully terminated with standard ablation once enrolled will be followed in a registry for 6 months, (adhering to the same post-procedure schedule as the patients that underwent intramural needle ablation). Two hundred subjects are

	expected to be enrolled in the study.
Clinical Sites:	Mount Sinai Hospital, New York, NY
Time Course:	Expected duration of patient enrollment is approximately 2 years.
Subject Description:	Subjects will only be eligible for this study if they are \geq 16 years of age and have a history or suspected history of ventricular arrhythmias.
Primary Endpoints:	
 1. Freedom from recurrent ventricular arrhythmias at 6 months 2. Procedural complications (death, stroke, myocardial infarction, heart failure, conduction abnormalities, pericardial effusion requiring drainage, hematoma, pseudoaneurysm)
Secondary Endpoints:	
 1. Post-ablation inducibility 2. Time to termination 3. Total duration of intramural needle ablation 4. All-cause mortality
	(For patients who have been re-enrolled after the six-month follow-up is complete, primary and secondary endpoints will be re-assessed at six months post-second procedure.)
Primary Analytical Analysis:	N/A
Secondary Analytical Analysis:	N/A
Study Sponsor:	[name]. Icahn School of Medicine at Mount Sinai [name]

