4 DEVICES AND PROCEDURES

4.1 HARDWARE / SOFTWARE / CATHETERS

The needle-tipped ablation catheter is a deflectable catheter with a distal bipole (dome and ring electrodes) with an extendable/retractable 27-gauge nitinol needle. The needle has a central lumen through which saline can be infused. It has an embedded thermocouple and a position sensor within the tip which is compatible with an electroanatomic mapping system (Carto; Biosense Webster). The needle can be extended or retracted to adjust the depth. It can be locked in position at the desired depth. In its fully retracted position, it is entirely within the catheter tip, whereas, when fully deployed, it extends 12 mm beyond the tip. The depth of extension can be preset and the needle can be locked in position with an adjustable plunge activator. During catheter manipulation, the needle is kept retracted and irrigated with 0.9% saline (with 2 U/mL heparin) at 1 mL/min.

Recording and pacing are possible from both the external electrodes and from the needle. Bipolar recordings are generated between the needle and ring electrode (filtered 30–500 Hz), and between the needle and an inferior vena cava electrode, as well (filtered 30–500 Hz, and separately, filtered 0.5–500 Hz).

At target sites of VT circuits, the catheter tip is placed roughly perpendicular to the endocardial surface. Infusion is discontinued and the needle is extended 7 to 9 mm into the myocardium. One ml of infusate (50% NaCl solution [with 2U/mL heparin], 50% iopamidol [76%]) is injected into the myocardium, after which heparinized saline (2 U/mL, 0.9% NaCl) is infused at 1 mL/min for 60 s. Myocardial staining with contrast is confirmed with fluoroscopy to ensure intramyocardial positioning and to rule out perforation. Temperature-controlled power is delivered for 60 to 90 s with temperature limited to 60°C and power limited to <35 W.

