6 ENDPOINTS

6.1 Primary Endpoint

1. Freedom from recurrent ventricular arrhythmias at 6 months, defined as sustained ventricular tachycardia lasting longer than 30 seconds or a decrease in ventricular arrhythmias (defined as unifocal PVCs, couplets, non-sustained VT) to less than 5000 ventricular beats per 24 hours and identified due to clinical symptoms, device interrogation, or 24-hour ambulatory monitoring.
2. Procedural complications (death, stroke, myocardial infarction, heart failure, conduction abnormalities, pericardial effusion requiring drainage, hematoma, pseudoaneurysm)

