8 SAMPLE SIZE

This safety and efficacy study will enroll up to 200 patients across 1 US center. This number has been determined on the basis of study feasibility and not by statistical means. In a similar trial, we have experienced a 66% screen failure rate; as such, with 200 patients enrolled, we expect to have approximately 70 evaluable patients who have undergone the INA procedure.

[figure not shown]

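### A procedure aborted for a complication before any ablation has no post-discharge follow-up and no stated place in the safety analysis

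*Combined protocol and SAP*

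**What the plan says.** **Follow-up.** Section 5 says "No follow-up will be performed with subjects who have no VT ablation during the procedure", and Section 9 repeats it. In both places it follows directly on the non-inducible case, which Section 5 words as "Patients whose VT is not inducible and no VT ablation is performed during the procedure will also be considered screen failures".

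**Screen failure.** The Protocol Summary has a wider rule: "Patients who do not undergo ablation of ventricular arrhythmias within 90 days of enrolling will be considered to be screen failures". It gives no reasons and no exceptions.

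**Order of steps.** Under Section 4.1 the needle is extended 7 to 9 mm and contrast is injected before power is delivered. At that point "Myocardial staining with contrast is confirmed with fluoroscopy to ensure intramyocardial positioning and to rule out perforation".

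**Safety endpoint.** Section 6.1 lists "Procedural complications (death, stroke, myocardial infarction, heart failure, conduction abnormalities, pericardial effusion requiring drainage, hematoma, pseudoaneurysm". Section 17 reports it as a percentage of the total study population, a term that is not defined. Section 8 forecasts that "with 200 patients enrolled, we expect to have approximately 70 evaluable patients who have undergone the INA procedure", without saying whether needle deployment without energy delivery counts as having undergone the procedure.

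**Event capture.** Table 1 marks adverse events at procedure, discharge, 2 weeks and 6 months. Section 10.4.1 requires a review before discharge. Section 11 sends all adverse events to the DMC and stops the trial if severe events attributed to the procedure exceed 15% of patients, again with no stated denominator.

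**The concern.** A patient can be harmed before any ablation is delivered: during vascular access, transseptal or subxiphoid puncture, mapping, or needle deployment. If the operator then stops, the patient has had no VT ablation in that procedure. Read literally, the follow-up rule ends scheduled contact at discharge. If the procedure is not repeated within 90 days, the Summary also makes the patient a screen failure.

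The reason for losing the patient would then be the kind of event that the co-primary safety endpoint counts. Two things are at stake. Late consequences of the complication have no scheduled contact at which they would be found. And an analyst who drops screen failures, which the text allows, would report a complication rate that is too low for a device whose new risk includes needle deployment.

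**Working it through.** **1. The plan's own figure.** Section 8 says of a similar trial that "we have experienced a 66% screen failure rate". Then 200 × (1 − 0.66) = 68 evaluable patients, against the stated figure of about 70, and 200 × 0.66 = 132 screen failures. The figure reproduces. There is no power calculation to check: "This number has been determined on the basis of study feasibility and not by statistical means".

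**2. Where an aborted procedure falls under the text**

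| Situation | Follow-up | Status |
|---|---|---|
| VT not inducible, no ablation | None (Sections 5, 9) | Screen failure (Sections 5, 9) |
| Complication at access or mapping, no ablation | None, read literally | Screen failure if not ablated within 90 days (Summary) |
| Straight to the needle after an earlier failed ablation, stopped before any energy | None, read literally | As above; evaluable status not stated |
| Standard ablation given and failed, needle step then stopped | Not barred, but in neither described follow-up group (standard success or needle ablation) | Not a screen failure; evaluable status not stated |

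The needle case therefore meets the no-follow-up rule only where no standard energy was given in that session. Sections 10.1 and 10.3 allow this route for patients with an earlier failed ablation. A perforation then enters the endpoint only through a listed component, such as an effusion that needs drainage.

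**3. Effect of omitting events.** The documents give neither a rate of aborted procedures nor an expected endpoint rate, so every event count below is an assumption. Omitting k such patients removes them from numerator and denominator: (x − k)/(n − k).

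- True 6/68 = 8.8%. With k = 1: 5/67 = 7.5%. With k = 2: 4/66 = 6.1%.

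Conversely, adding k omitted patients to x events among 70 gives (x + k)/(70 + k):

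| x of 70 | k = 0 | k = 1 | k = 3 |
|---|---|---|---|
| 5 | 7.1% | 6/71 = 8.5% | 8/73 = 11.0% |
| 7 | 10.0% | 8/71 = 11.3% | 10/73 = 13.7% |
| 10 | 14.3% | 11/71 = 15.5% | 13/73 = 17.8% |

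**4. The 15% rule.** If the events are severe and attributed to the procedure, one added patient moves 10/70 (14.3%) to 11/71 (15.5%), across the line. Among 20 treated patients, 3/20 = 15.0% is not above the line and 4/21 = 19.0% is. The interim look comes at 20 enrolled, which at the forecast rate is 20 × 0.34 = 6.8, about 7 evaluable patients.

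**5. The denominator.** Section 9 counts patients as enrolled at consent. If the total study population means everyone enrolled, 10 events are 10/200 = 5.0%, against 10/70 = 14.3% among evaluable patients. The first reading keeps the aborted case but dilutes the rate with patients who were never treated. The second may lose it. Neither gives the rate among patients exposed to the needle catheter.

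**The case against.** The strongest reply is that nothing in the plan removes a recorded event from the analysis. The sentence in Sections 5 and 9 limits follow-up only. Acute complications are recorded at the procedure and reviewed before discharge, all adverse events go to the DMC, and serious ones go to the IRB and the coordinating center. With enrollment at consent and a total study population denominator, a complication in an aborted procedure can be read as counting. The figure of about 70 evaluable patients is a feasibility forecast, not a definition of an analysis set. The follow-up sentence comes straight after the non-inducible case and may have been meant for that group alone.

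Most of this stands. A reader might infer that the plan excludes these complications from the safety endpoint and biases the rate by some 30%. The documents do not support that. Exclusion is one reading of undefined terms. The 30% comes from 6/68 against 4/66, that is (8.8 − 6.1)/8.8 = 31%, and needs two of six assumed events to be aborted cases. Section 12 gives 1.5% for perforation with effusion or tamponade over the whole procedure, so 68 × 0.015 = 1.02 such events would be expected at any stage. The roughly 4% for tamponade applies only with epicardial ablation. No share before energy delivery is given.

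The reply does not meet two points. Recording an event does not place it in an analysis set, and none is defined. And the follow-up sentence is general as written, so discharge is the last scheduled contact for these patients.

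**Conclusion.** The point holds in a limited form. As written, the plan ends scheduled follow-up at discharge for any patient with no ablation in the procedure, and can make that patient a screen failure, even when a complication was the reason for stopping. Whether the acute event counts in the safety endpoint is left open, not decided against.

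The likely effect on the rate is small in absolute terms: about 1.3 percentage points for one event in the assumed 6/68 case (8.8% − 7.5%). That is well inside sampling error. The exact 95% interval is 7.1% to 24.7% for 10/70 and 8.0% to 26.0% for 11/71. It matters mainly because a single event can decide whether the 15% rule is met, and because safety is a co-primary endpoint. These sizes rest on assumed event counts. The gap in follow-up and the missing definitions rest on the text alone. This is a cheap improvement worth making, not a defect that undermines the trial.

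**What to change.** 1. **Sections 5 and 9, and the 90-day sentence in the Protocol Summary.** Limit the no-follow-up and screen-failure rules to patients with no ablation, no needle catheter introduced and no adverse event by discharge. Everyone else in whom the procedure was started keeps the existing 2-week and 6-month schedule.
2. **Sections 11 and 17.** Define the safety set as all patients in whom the procedure was started, and say what marks the start. A set limited to needle-catheter patients would miss complications of access and mapping. Report as a subset all patients in whom the needle catheter was introduced, whether or not energy was delivered, so that the device's own risk is not diluted.
3. **Sections 8, 11 and 17.** Say what evaluable and total study population mean, and state the denominator for the safety endpoint and for the 15% rule.

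The cost is wording, a handful of extra follow-up contacts, and possibly a slightly higher reported complication rate. The sample size does not change.
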